##### 4.1.2.2 Safety

See section 8.2 and section 9.3.3 of the protocol

##### 4.1.2.3 Transmission

See section 8.1.2 and section 9.3.3 of the protocol

#### 4.1.3 Exploratory Endpoints and Assessment Methods

##### 4.1.3.1 [REDACTED]

[REDACTED]

##### 4.1.3.2 [REDACTED]

[REDACTED]

#### 4.1.3.3 [REDACTED]

#### 4.1.4 Safety Exploratory Endpoints and Assessment Methods

No safety Exploratory Endpoints

### 4.2 Complementary Information on Derived Endpoints: Calculation Methods

#### 4.2.1 Vaccine Virus Transmission

Vaccine virus transmission is defined as presence of detected vaccine virus confirmed by RSVt qRT-PCR assay (vaccine virus shedding  $\geq$  LOD) in pediatric participants receiving placebo and ad-hoc close contact participants.

Detected viable RSV virus is defined as values from the plaque assay  $\geq$  LOD.

#### 4.2.2 Vaccine virus shedding

Detected virus shedding is defined as vaccine virus shedding  $\geq$  LOD by RSVt qRT-PCR assay.

Quantified virus shedding is defined as vaccine virus shedding  $\geq$  LLOQ by RSVt qRT-PCR assay.

#### 4.2.3 Infectivity

Infectivity is defined as detection of vaccine virus strain in any post-vaccination nasal swab sample by RSVt qRT-PCR and/or a  $\geq$  4-fold rise from baseline (D01) in RSV A serum nAb titers and/or RSV serum anti-F IgG Ab titers.

- Infectivity after vaccination 1: Detection of vaccine virus shedding ( $\geq$  LOD) by RSVt qRT-PCR at any post-vaccination 1 NS samples (D04, D08, D11, D15, D18 and D22) and/or a  $\geq$  4-fold rise from baseline (D01) in RSV A serum nAb titers and/or RSV serum anti-F IgG Ab titers at D57
- Infectivity after vaccination 2: Detection of vaccine virus shedding ( $\geq$  LOD) by RSVt qRT-PCR at any post-vaccination 2 NS samples (D64 and D71) and/or a  $\geq$  4-fold rise from baseline (D01) in RSV A serum nAb titers and/or RSV serum anti-F IgG Ab titers at D85
- Infectivity after any vaccination: Detection of vaccine virus shedding ( $\geq$  LOD) by RSVt qRT-PCR at any post vaccination NS samples (D04, D08, D11, D15, D18, D22, D64 and D71) and/or a  $\geq$  4-fold rise from baseline (D01) in RSV A serum nAb titers and/or RSV serum anti-F IgG Ab titers at D57 and /or D85

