2.3.2 Benefits from Study Participation

Pediatric participants randomized in the group to receive the RSVt vaccine may benefit from coverage against respiratory syncytial virus and may be less likely to develop RSV associated pneumonia or RSV related severe illness and/or hospitalization.

However, as with all vaccines, vaccination with the investigational vaccine may not protect individuals 100%.

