For any pediatric participants presenting clinical symptoms of ARI during the intervention phase (D1 to D85), an additional nasal swab may be collected to identify potential WT RSV infection with Multiplex RT-PCR. Some of the regular nasal swabs from symptomatic children in which no vaccine virus was detected may also be tested for WT RSV strain. If ARI is diagnosed < 2 days before or after a scheduled nasal swab, then the planned nasal swab will be used for WT RT-PCR testing. The ad-hoc close contact participants with any clinical symptoms of ARI within 28 days after study intervention administration of the close contact pediatric participant should have an illness visit.

Consideration of the RSV Season

The VAD00014 study is planned to start during Quarter (Q)4 2022, regardless of the actual start of the RSV season. In the Northern Hemisphere, the RSV season usually begins in late Q3 or early Q4 and lasts about 5 months. However, due to the increased variability in the RSV epidemiology since the beginning of the SARS-CoV-2 pandemic, it is difficult to evaluate the extent to which the RSV season will impact the clinical study. To mitigate the impact of the RSV season during the study, ARI will be followed up to 28 days after the second study intervention administration for all pediatric participants. Baseline blood sample will be used as an indication of possible previous RSV exposure.

Non-exclusion of pregnant women participants

Ad-hoc close contact participants can include pregnant females as they will only provide nasal swabs and will not receive any study intervention. Thus, VAD00014 study can be considered a safety surveillance study for the ad-hoc close contact participants and therefore pregnant women are not excluded from participating in the study.

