### **3.4.3 Secondary Endpoints**

#### **3.4.3.1 Immunogenicity**

RSV A serum neutralizing antibody titers and RSV serum anti-F IgG antibody titers will be summarized at each timepoint (D01, D57, and D85) in pediatric participants by study intervention group, including but not limited to:

- GMTs and 95% CI
- Geometric mean titers ratio (GMTR) relative to pre-vaccination titer and 95% CI.
- Number and percentage of participants with pre-vaccination titers  $<$  LLOQ or  $\geq$  LLOQ
- Number and percentage of participants with post-vaccination titer  $\geq$  2-fold rise or 4-fold rise
- Reverse cumulative distribution curves (RCDCs)

Immunogenicity analyses will be presented on the FAS.

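### A 4-fold antibody rise counts as vaccine infectivity even after a detected wild-type RSV infection, and no visible rule uses the planned wild-type RT-PCR results

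*SAP*

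**What the plan says.** SAP 4.2.3 has two limbs joined by and/or. The virological limb is specific to the vaccine: "Infectivity is defined as detection of vaccine virus strain in any post-vaccination nasal swab sample by RSVt qRT-PCR". The serological limb is at least a "4-fold rise from baseline (D01) in RSV A serum nAb titers and/or RSV serum anti-F IgG Ab titers", read at D57 after vaccination 1. After vaccination 2 the same rise is read at D85, again against D01. Either limb is enough.

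SAP 3.4.3.1 summarises the same two antibodies as GMT, GMTR and fold-rise rates ("Number and percentage of participants with post-vaccination titer" at least 2-fold or 4-fold above baseline). The objective in SAP Table 2.1 describes these as responses to the study intervention. On the population, 3.4.3.1 says: "Immunogenicity analyses will be presented on the FAS". SAP 3.4.1 uses the FAS for infectivity too.

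Protocol 4.2 anticipates wild-type RSV. It says "it is difficult to evaluate the extent to which the RSV season will impact the clinical study" and names ARI follow-up to 28 days after the second dose as the mitigation. For a child with ARI between D1 and D85, "an additional nasal swab may be collected to identify potential WT RSV infection with Multiplex RT-PCR". SAP Table 3.1 gives wild-type infection its own summary row, and SAP 3.5 schedules wild-type RT-PCR data for the second step of the interim analysis.

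**The concern.** By Protocol 2.2, the vaccine virus is defined by the NS2 deletion and changes in the L protein. RSV A neutralizing antibody and anti-F IgG are not directed at either, so a rise in them does not show which RSV caused it. A child who catches wild-type RSV after D01 and responds 4-fold is recorded as infected by the vaccine virus, even if that wild-type infection was confirmed by the trial's own testing. The same titers also raise the GMT, GMTR and fold-rise figures.

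In the placebo arm such a child would appear as a case of vaccine infectivity without ever meeting vaccine virus. In the vaccine arm the infectivity rate is overstated among children in whom the vaccine did not take. The information that could separate these cases is planned for collection, but no visible infectivity or immunogenicity rule uses it.

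**Working it through.** **1. Is there a rule that removes these rises?** The visible places where one could stand are:

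- FAS (SAP 3.3): randomized and dosed at least once; nothing on wild-type RSV after D01.
- PPAS (SAP 3.3): excludes RSV exposure before D01 only, and is used for transmissibility, not for infectivity or immunogenicity.
- Missing data (SAP 3.4.6.2): no imputation and no outlier search; nothing on titers after a wild-type infection.
- Fold-rise (SAP 4.2.6.2): deals only with values below LLOQ and missing values.
- Infectivity definition (SAP 4.2.3): no exception.

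No visible rule removes them.

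**2. Windows.** The PCR limb looks at D04 to D22 and at D64 and D71. The serological limb covers everything from D01 to D57 and from D01 to D85. No planned swab falls between D22 and D64. Take a wild-type infection at about D40. It can give a 4-fold rise at D57 and so count after vaccination 1. If the titer is still 4-fold above D01 at D85, it counts again after vaccination 2.

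**3. Size.** The plan states no figure to reproduce; the sample size rests on feasibility and all analyses are descriptive. Inputs:

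- n = 50 per arm (SAP 3.2).
- a = wild-type attack rate between D01 and the blood draw: assumed 5%, 10%, 20%.
- r = probability of a 4-fold rise after wild-type infection: assumed 80%.
- t = true vaccine take: 88% is the infectivity reported in one study of RSV-seronegative children (Protocol 2.2); 50% and 70% are illustrative, because this trial does not screen on serostatus.

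Let b = a × r. With no transmission, placebo infectivity is b. If b is the same in both arms and independent of take, vaccine-arm infectivity is t + (1 − t)b, an inflation of (1 − t)b.

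| a | b = 0.8a | placebo scored infected, 50b | inflation, t = 50% | t = 70% | t = 88% |
|---|---|---|---|---|---|
| 5% | 4% | 2 of 50 | 2.0 points | 1.2 | 0.5 |
| 10% | 8% | 4 of 50 | 4.0 points | 2.4 | 1.0 |
| 20% | 16% | 8 of 50 | 8.0 points | 4.8 | 1.9 |

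In the last row, at t = 50%, the vaccine arm reads 0.50 + 0.50 × 0.16 = 58% (29 of 50) instead of 50% (25 of 50). At t = 88% it reads 0.88 + 0.12 × 0.16 = 89.9%, about 45 of 50 instead of 44. If b itself is allowed to run from 5% to 30%, the placebo count is 50 × 0.05 = 2.5 to 50 × 0.30 = 15.

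**The case against.** **Transmission.** A reader might infer that the transmission results are contaminated. They are not. SAP 4.2.1 defines transmission by RSVt qRT-PCR at or above LOD, and SAP 3.4.2.1 and 3.4.3.3 report it that way after each dose. Serology plays no part, and no primary endpoint is touched.

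**Season.** A reader might also infer that the whole trial runs in RSV season. Protocol 4.2 plans a Q4 2022 start whatever the season does, with a season of about 5 months. SAP 3.5 has an interim cut for randomization up to 21 July 2023, with a later interim on all participants. Exposure is in season for only part of the follow-up.

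**Distorted contrast.** It is tempting to say that a vaccine-placebo comparison is biased, and more so through placebo. No between-arm contrast is visible; the summaries are by arm. The only basis for a difference in wild-type risk is the statement in Protocol 2.3.2 that vaccinees "may benefit from coverage against respiratory syncytial virus", which gives no estimate.

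**Other displays.** Vaccine-virus detection, fold-rise rates and wild-type infections are each tabulated by arm, so a careful reader sees the pieces. They are marginal tables, however, and do not show which infectivity cases are serology-only or followed wild-type RSV.

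**Placebo as background.** The placebo arm gives a rough background rate, which limits the harm. It does not correct the vaccine-arm rate, and a serology-only rise in placebo could come from wild-type or transmitted vaccine virus.

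**Redaction.** Infectivity is not among the visible primary or secondary endpoints. SAP 3.4.4 and 4.2.7 are redacted and could hold a split by limb or a wild-type exclusion. SAP 3.4.3.1 also says its list is not exhaustive. This limits how firmly an omission can be claimed, but not what the visible definition in 4.2.3 does.

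**Conclusion.** The point stands for infectivity and for the secondary immunogenicity summaries. As written, SAP 4.2.3 can classify a documented wild-type RSV infection as vaccine infectivity, possibly after both doses, and SAP 3.4.3.1 takes the same titers as response to the study intervention.

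The size rests on assumptions. The attack rate and the response to wild-type RSV are not in the documents; the 80% in Protocol 2.2 is the neutralizing response to the vaccine in seronegative children, a different quantity. Within the assumed range, 2 to 8 of 50 placebo children are affected. Vaccine-arm inflation runs from about 0.5 point (88% take, 5% attack rate) to 8 points (50% take, 20% attack rate). It would be smaller still if vaccinees were protected from wild-type RSV.

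**What to change.** 1. In SAP 4.2.3 and its tables, report infectivity by arm as PCR-confirmed and serology-only, beside the planned composite.
2. Alongside the planned FAS results, add a sensitivity analysis for wild-type RSV detected between D01 and the blood draw in question. The serological limb is not credited for that draw; a child with vaccine virus by PCR stays counted. In the GMT, GMTR and fold-rise tables, titers from that draw are set to missing.

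The cost is SAP wording and one repeated table set, from results already planned. There are three drawbacks. A few children are lost, including some who may have responded to the vaccine before catching wild-type RSV. Mild or untested wild-type infections remain in, because testing is optional and triggered by symptoms. The exclusion also follows a post-randomization event that may differ by arm. For these reasons the analysis should supplement the planned tables and not replace them.

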deletions of the gene encoding the RSV interferon / apoptosis antagonist NS2 protein (Δ NS2). Deletion of NS2 gene attenuates the virus and may enhance immunogenicity. RSV Δ NS2/ Δ 1313/I1314L vaccine additionally contains a genetically stabilized attenuating and temperature sensitivity mutation in the L protein (codon deletion Δ 1313, as well as a missense mutation I1314L that prevents a de-attenuating mutation that otherwise can occur at position 1314). The RSV Δ NS2/ Δ 1313/I1314L temperature sensitivity translates into a shut-off of virus replication at 38°C-39°C.

Prior to RSV Δ NS2/ Δ 1313/I1314L vaccine, three RSV vaccine viruses with the NS2 gene deletion (rA2cp Δ NS2, rA2cp248/404 Δ NS2, and rA2cp530/1009 Δ NS2) had been evaluated in clinical studies (6). The rA2cp Δ NS2 candidate was over-attenuated for adults but under-attenuated for use in young children, whereas both rA2cp248/404 Δ NS2 and rA2cp530/1009 Δ NS2 were over-attenuated and insufficiently immunogenic in seronegative children.

Sanofi's investigational RSV Δ NS2/ Δ 1313/I1314L vaccine (hereafter referred to as RSVt vaccine) is the same construct as the NIH RSV Δ NS2/ Δ 1313/I1314L vaccine. The vaccines differ in formulation and mode of intranasal administration. The RSVt vaccine is being developed for the pediatric population.

Phase I Clinical Data (NIH RSV Δ NS2/ Δ 1313/I1314L)

A Phase Ia study was conducted by the National Institutes of Health (NIH) in RSV seronegative children aged 6 to 24 months (n=20) who received NIH RSV Δ NS2/ Δ 1313/I1314L vaccine at the 10^6 PFU dose level. This study showed that the 10^6 PFU dose level was safe, had good infectivity (100% of vaccinated participants infected) and immunogenicity (80% of participants with a \geq 4-fold rise in neutralizing antibody titers), and primed for a strong anamnestic response to wildtype (WT) RSV infection in the post-RSV season surveillance (20).

Another study aiming at describing the safety and immunogenicity of the NIH RSV Δ NS2/ Δ 1313/I1314L vaccine in RSV-seronegative children (IMPAACT 2018, NCT03227029 / NCT03422237) confirm the previous results such as the good safety profile, high infectivity (88%) and genetic stability of the candidate (21).

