In addition, pediatric participant's close contacts who experience an ARI in the 28 days following the study intervention administration may be asked to provide a nasal swab. The pediatric participant's close contacts are any persons who are in the same room as the pediatric participant for more than 4 hours a day for at least 3 days a week. These may include children attending the same daycare center, daycare center staff in contact with pediatric participants, or household members of pediatric participants. They are hereafter referred to as the ad-hoc close contact participants.

Each pediatric participant will provide a blood sample at baseline, and after each study intervention administration, ie, 56 days after the first administration (D57, pre-administration 2) and 28 days after the second administration (D85). The blood sample collected at Visit 01 will be used to determine the pediatric participant's RSV serostatus at baseline. The blood samples collected at Visit 08 and Visit 11 will be used to assess the pediatric participants' immune response after each administration. The RSVt vaccine immunogenicity will be evaluated using an RSV A microneutralization assay and an RSV anti-F IgG ELISA.

The safety profile of the study interventions will be assessed in all pediatric participants after each administration with the collection of:

- immediate AEs occurring within 30 minutes
- solicited administration site and systemic reactions within 21 days after each study intervention administration
- unsolicited AEs, AESIs, and MAAEs within 28 days after each study intervention administration
- serious AEs (SAEs) throughout the study

For the ad-hoc close contact participants, MAAEs related to study procedures will be followed up to 28 days after each study procedure and collected in source documents.

The following AESIs will be collected:

[REDACTED]

[REDACTED]

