4.3 Justification for Dose

Justification for 2 doses administration schedule

There are several published studies evaluating 2 or 3 administrations of attenuated RSV or parainfluenza virus type 3 (PIV3) candidate vaccines (4) (5) (8) (24) (25) (26) (27) (28) (29). Generally, there was a high level of restriction of the second administration, and limited serum immune responses. The main effect was vaccine infectivity in the individuals who did not respond to the first administration. Two administrations of RSV Δ NS2/ Δ 1313/I1314L may improve the infectivity of either dose.

Justification for vaccine dose

The vaccine dose has been selected based on benefit/risk assessment based on results obtained the first Phase I/II VAD00001 study conducted in infants and toddlers 6 to 18 months of age receiving 2 doses of RSVt vaccine at concentration of [REDACTED]

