**Table 1.2: Schedule of activities for pediatric participants**

Phase II Study, 11 Planned Visits, 2 Vaccinations, 3 Blood Samples, 9 Planned Nasal Swabs, One 6-Month Safety Follow-up Phone Call, approximately 8 Months' Duration Per Pediatric Participant

Visit/Contact*	Collection of information in the CRF	V01	V02	V03	V04	V05	V06	V07	V08	V09	V10	V11	Safety followup phone call	Illness Visit‡‡
Study timelines days (D)		D01	D04	D08	D11	D15	D18	D22	D57	D64	D71	D85	D237	
Visit Interval			V01 + 3d	V01 + 7d	V01 + 10d	V01 + 14d	V01 + 17d	V01 + 21d	V01 + 56d	V08 + 7d	V08 + 14d	V08 + 28d	V08 + 6 months	
Time windows (days)		NA	[+1]	[+1]	[+1]	[+1]	[+1]	[+1]	[+7]	[+1]	[+1]	[+7]	[+14]	
Visit procedures:														
Informed consent	X	X												
Inclusion/exclusion criteria	X	X												
Collection of demographic data	X													
Collection of medical history	X Significant Medical History	X												
Physical examination	X	X							X					
Vital signs†	X	X							X					
Rapid COVID-19 test	X	X							X					

Visit/Contact*	Collection of information in the CRF	V01	V02	V03	V04	V05	V06	V07	V08	V09	V10	V11	Safety followup phone call	Illness Visit‡‡
Study timelines days (D)		D01	D04	D08	D11	D15	D18	D22	D57	D64	D71	D85	D237	
Visit Interval			V01 + 3d	V01 + 7d	V01 + 10d	V01 + 14d	V01 + 17d	V01 + 21d	V01 + 56d	V08 + 7d	V08 + 14d	V08 + 28d	V08 + 6 months	
Time windows (days)		NA	[+1]	[+1]	[+1]	[+1]	[+1]	[+1]	[+7]	[+1]	[+1]	[+7]	[+14]	
Collection of reportable concomitant medications/vaccinations	X								X					X
Randomization/allocation of participant number	X	X												
Dose number	X	X							X					
Blood sampling (BL) [5 mL]	X	BL0001 Pre-vac1							BL0002 Pre-vac2			BL0003		
Nasal swab (NS)‡	X	NS0001 Pre-vac1	NS0002	NS0003	NS0004	NS0005	NS0006	NS0007		NS0008	NS0009			UN0001 to UN000X
Vaccination (vac)	X	VAC1							VAC2					
Immediate surveillance (30 min)§	X	X							X					
DC provided**		DC1							DC2					
DC reviewed††			DC1	DC1	DC1	DC1	DC1	DC1	DC1	DC2	DC2	DC2		
DC collected									DC1			DC2		
MA provided												MA		
MA reviewed												MA		
Collection of solicited administration site and systemic reactions	X	From D01 to D22							From D57 to D78					

Visit/Contact*	Collection of information in the CRF	V01	V02	V03	V04	V05	V06	V07	V08	V09	V10	V11	Safety followup phone call	Illness Visit†‡
Study timelines days (D)		D01	D04	D08	D11	D15	D18	D22	D57	D64	D71	D85	D237	

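### Infectivity after vaccination 2 is measured from D01, before dose 1, so a dose-1 or wild-type rise that persists to D85 counts as infection after dose 2

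*SAP*

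**What the plan says.** SAP 4.2.3 defines infectivity three times.

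- **After vaccination 1:** virus detected in any swab from D04 to D22, and/or a rise of at least 4-fold from D01 in RSV A neutralizing antibody and/or "RSV serum anti-F IgG Ab titers at D57".
- **After vaccination 2:** virus detected "by RSVt qRT-PCR at any post-vaccination 2 NS samples (D64 and D71) and/or a" rise of at least 4-fold, specified as a "4-fold rise from baseline (D01) in RSV A serum nAb titers and/or RSV serum anti-F IgG Ab titers at D85".
- **Cumulative:** "Infectivity after any vaccination: Detection of vaccine virus shedding" in any post-vaccination swab, and/or the same D01-based rise at D57 and/or D85.

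A blood sample is taken immediately before dose 2. The SAP schedule (Table 1.2) lists it as "BL0002 Pre-vac2", and Protocol 4.1 places the post-baseline samples at "56 days after the first administration (D57, pre-administration 2) and 28 days after the second administration (D85". Both antibodies are summarized at D57 (SAP 3.4.3.1).

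Infectivity is analysed on the FAS (SAP 3.4.1), which requires only one administration (SAP 3.3). The fold-rise rule (SAP 4.2.6.2) deals with values below the LLOQ and with missing values. It names no reference visit and does not set aside children who already met the criterion at D57.

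**The concern.** D01 is the right reference for the first dose and for the cumulative measure. For the second dose it is not, because the interval from D01 to D85 contains both doses. The two arms of the definition are joined by and/or, so serology alone is enough. A child who responded to dose 1 and is still at least 4-fold above D01 at D85 is counted whatever dose 2 did. The same holds for a child in either group who had a wild-type RSV infection between D01 and D57. A child who stopped after one dose but gave a D85 sample could also be counted, since the FAS does not require a second dose and Protocol 7.1.2 keeps definitively discontinued children in immunogenicity follow-up.

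This matters because the second dose is where the question of new take arises. Protocol 4.3, summarizing earlier RSV and PIV3 candidates, says "Generally, there was a high level of restriction of the second administration", and that the main effect was in children who had not responded to the first dose. Protocol 4.2 expects less shedding after dose 2. If few swabs are positive at D64 and D71, the serological arm may supply most of the count, and that arm cannot separate a new response from a persisting one.

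**Working it through.** The documents give no infectivity figure for this trial and no sample-size calculation, so there is no stated number to reproduce. The check has two parts.

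**1. Apply the rule to individual titers.** Take titers at D01, D57 and D85, with no virus at D64 or D71. The SAP criterion is D85/D01 ≥ 4. The alternative is D85/D57 ≥ 4.

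| D01, D57, D85 | D85/D01 | SAP: after vaccination 2 | D85/D57 | D57 reference |
|---|---|---|---|---|
| 10, 80, 80 | 8 | infected | 1 | not infected |
| 10, 80, 60 | 6 | infected | 0.75 | not infected |
| 10, 80, 40 | 4 | infected | 0.5 | not infected |
| 10, 80, 39 | 3.9 | not infected | 0.49 | not infected |
| 10, 80, 320 | 32 | infected | 4 | infected |
| 10, 10, 40 | 4 | infected | 4 | infected |

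The first three children had a flat or falling titer after dose 2 and are still counted. The fourth waned below 4-fold over D01 and is not. So the error concerns responders whose rise persists to D85, not all dose-1 responders.

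**2. Expected counts.** Inputs:

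- n = 50 per group (SAP 3.2), taking all as evaluable.
- r = share with a serological response after dose 1. The only figure in the documents is 80% with a neutralizing rise of at least 4-fold, in 20 seronegative children given the NIH product (Protocol 2.2). Children here are not screened for serostatus (Protocol 4.2), so 80% is treated as an upper scenario and the assumed range is 20–80%.
- s = share of those responders still at least 4-fold over D01 at D85 with no dose-2 effect. Not given; assumed 50–100%.
- t = true dose-2 infection rate. Not given; assumed.

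Taking t as independent of dose-1 response, and every true dose-2 infection as detected:

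SAP rate = t + (1 − t) × r × s

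| r | s | t | SAP rate | SAP count | True count |
|---|---|---|---|---|---|
| 20% | 50% | 0 | 0.20 × 0.50 = 10% | 5/50 | 0/50 |
| 40% | 75% | 0 | 0.40 × 0.75 = 30% | 15/50 | 0/50 |
| 80% | 50% | 0 | 0.80 × 0.50 = 40% | 20/50 | 0/50 |
| 80% | 75% | 0 | 0.80 × 0.75 = 60% | 30/50 | 0/50 |
| 80% | 100% | 0 | 0.80 × 1.00 = 80% | 40/50 | 0/50 |
| 80% | 75% | 10% | 0.10 + 0.90 × 0.60 = 64% | 32/50 | 5/50 |

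With a D57 reference, t = 0 and flat or waning titers, the serological count is 0/50 (Clopper-Pearson 95% CI 0 to 7.1%).

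**The case against.** **The item may be meant cumulatively, and it names D01 openly.** The reference is indeed explicit. But the swab arm uses only the two swabs after dose 2 and ignores those from D04 to D22, and a separate any-vaccination item already gives the cumulative result. The item therefore reads as dose-specific, with a serological arm that is not.

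**Dose-2 information is reported elsewhere.** This stands. Detected and quantified shedding at D64 and D71 is tabulated by group (SAP 3.4.2.2), and GMTs and reverse cumulative curves are given at D57 and D85 (SAP 3.4.3.1). A careful reader could see from these that dose 2 did little. They do not correct the composite, but they limit the damage.

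**The endpoint carries little visible weight.** This also stands. Infectivity is not among the visible primary or secondary endpoints, every analysis is descriptive, and the exploratory sections are redacted, so a tabulation by dose-1 status may exist unseen.

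**A D57 reference has its own bias, downward.** Titers of 10, 20, 60 are 6-fold over D01 but 3-fold over D57. Titers of 10, 80, 300 are 3.75-fold over D57. Without virus at D64 or D71, both would become not infected. That is why a change of reference should come with results by dose-1 status.

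**Readings that go too far.** A reader might infer that the table would mislead a choice between one and two doses for Phase III. The documents assign no such decision to this trial: every pediatric participant is scheduled for two administrations, there is no one-dose arm, and one versus two administrations belongs to VAD00001. A reader might also infer that the table is bound to show high dose-2 infectivity. The 80% comes from a small seronegative sample given a product that differs in formulation and mode of administration, and persistence to D85 is given nowhere. Nor does the protocol predict strong restriction for this vaccine; it reports it for earlier candidates and expects only lower shedding here.

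**Conclusion.** The concern holds as a should-fix. As written, infectivity after vaccination 2 counts any child whose dose-1 or wild-type rise is still at least 4-fold over D01 at D85 in either antibody, so it is biased upward as a measure of dose-2 take. The direction follows from the definition alone. The size does not: the 10–80% false floor rests on assumed response and persistence and on zero true dose-2 infections, and is illustrative. The visible primary and secondary endpoints are unaffected.

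**What to change.** In SAP 4.2.3, among children who received dose 2, define infectivity after vaccination 2 as virus detected at D64 or D71 and/or a rise of at least 4-fold from D57 (before dose 2) to D85 in either antibody. Report it also by infectivity status after vaccination 1, in particular among children not infected after dose 1. Keep the D01-based rule only for infectivity after any vaccination.

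The cost is a change to one definition, one derived variable and one summary by dose-1 status, made before database lock. No new samples or assays are needed, and the LLOQ rule in SAP 4.2.6.2 applies unchanged with D57 as the denominator.

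Two limits remain and should be stated with the result. True dose-2 responses can be missed in children with raised D57 titers, which the split by dose-1 status helps to show. Wild-type infection between D57 and D85 can still produce a rise; the placebo column gives an indication of that background.
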